1.2 OBJECTIVES

General Objective:

To find out the effectiveness thoracic mobility exercise compared with manual release technique in minimizing upper back pain

Specific Objective:

- To evaluate correlation between the sociodemographic factors and pain intensity of participants in experimental and control group.
- To evaluate the effectiveness of thoracic mobility exercise and manual release technique in improving upper back pain intensity
- To evaluate the effectiveness of thoracic mobility exercise and manual release technique in improving upper thoracic mobility
- To evaluate the effectiveness of thoracic mobility exercise and manual release technique in improving trunk upper back muscle strength
- To evaluate the effectiveness of thoracic mobility exercise and manual release technique in improving disability

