2. DESIGN AND METHOD

2.1 Study Site:

Study will be conducted University of Peradeniya.

2.2 Study Population:

Undergraduates who are currently having upper back pain for more than seven days will be selected as sample. Participants who will have sub-acute and chronic pain which means who will have pain more than a week or seven days will be selected as sample and who have subjected to any recent surgeries, recent fractures, accidents or injuries in upper back will be excluded from the study.

2.3 Study Setting:

Study will be conducted in Service unit of Department of physiotherapy at University of Peradeniya.

2.4 Study Design:

This study is a Randomized Control Trial, Double- Blinded study. Participants and assessors will be blinded. Participants will be allocated randomly in to two groups which are experimental group which will receive thoracic mobility exercises and control group which will receive myofascial release and joint mobilization treatment.

2.5 Hypothesis:

1. Hypothesis about difference in baseline characteristics of participants between control and experimental groups

Null Hypothesis: $H_0: \mu_1 - \mu_2 = 0$

There is no difference in baseline characteristics of participants between experimental and control group.

Alternate Hypothesis: $H_1: \mu_1 - \mu_2 \neq 0$

There is a difference in baseline characteristics of participants between experimental and control group

2. Hypothesis about differences in pain intensity between control group and experimental group.

Null Hypothesis: $H_0: \mu_1 - \mu_2 = 0$

There is no difference in pain intensity of participants between experimental and control group.

Alternate Hypothesis: $H_1: \mu_1 - \mu_2 \neq 0$

There is a difference in pain intensity of participants between experimental and control group

3. Hypothesis about differences in thoracic mobility (Range of Motion) between control group and experimental group.

Null Hypothesis: $H_0: \mu_1 - \mu_2 = 0$

There is no difference in thoracic mobility of participants between experimental and control group.

Alternate Hypothesis: $H_1: \mu_1 - \mu_2 \neq 0$

There is a difference in thoracic mobility of participants between experimental and control group

4. Hypothesis about differences in muscle strength of spinal extensors between control group and experimental group.

Null Hypothesis: $H_0: \mu_1 - \mu_2 = 0$

There is no difference muscle strength of spinal extensors of participants between experimental and control group.

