Personal details of the participants will be collected separately for the concealed allocation and participants will be identified by code number. Participants' age, gender, height, weight, BMI, family size, bread winner of the family, monthly income and financial support for the study will be collected in the demographic data section. In third section, questions related to occurrence of pain, pain duration and treatments which were undertaken for the pain will be collected from the participants.

VAS scale will be used to measure the intensity of pain in different situations which include present pain intensity, in sitting, in forward bending, in standing, in walking, in sleeping, in transferring and during day to day activities. Visual Analogue Scale will be used to measure the pain intensity. Subjects will be asked to mark the number between 0 and 10 that fits best to their pain intensity. Zero indicates 'no pain at all' whereas 10 represents 'the worst pain ever possible' (Figure 1). Measurement will be obtained in the baseline and at the end of two weeks.

[figure not shown]

Figure 1- VAS Scale

Thoraco-Lumbar flexion and Extension of thoracic spine Range of Motion will be taken in the fourth section. Measurement will be taken by using measuring tape. Measurement will be taken at the baseline and after two weeks. In the fourth section, muscle strength of thoracic spine extensors will be measured using Oxford-Grading Scale. Measurement will be taken at the baseline and after two weeks. The Oxford Muscle Scale is a numerical rating scale used to quantify the power or strength produced by the contraction of a muscle. The scale was originally developed by a UK government research group called the Medical Research Council (MRC). Reliability of the scale

explained by Intraclass Correlation Coefficient (ICC) and Interrator Reliability. It shows high ICC coefficient of 0.95 (ranging from 0.92 to 0.97) (Hermans et al., 2012).

Muscle Strength Grading Scale (Oxford Scale)	
0/5	No Contraction
1/5	Visible/palpable muscle contraction but no movement
2/5	Movement with gravity eliminated
3/5	Movement against gravity only
4/5	Movement against gravity with some resistance
5/5	Movement against gravity with full resistance

Table 1

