In the sixth section, The Pain Self-Efficacy Questionnaire (PSEQ) is a 10-item questionnaire developed to assess the confidence people with ongoing pain have in performing activities while in pain. The PSEQ has high internal consistency (0.92 Cronbach's alpha) and test-retest reliability is high of a 3-month period.

	0 "not at all confident"	1	2	3	4	5	6 "completely confident"
1. I can enjoy things, despite the pain.							
2. I can do most of the household chores (e.g. tidying-up, washing dishes, etc.), despite the pain.							
3. I can socialise with my friends or family members as often as I used to do, despite the pain.							

4. I can cope with my pain in most situations.						
5. I can do some form of work, despite the pain. ('work' includes housework, paid and unpaid work).						
6. I can still do many of the things I enjoy doing, such as hobbies or leisure activity, despite pain.						
7. I can cope with my pain without medication.						
8. I can still accomplish most of my goals in life, despite the pain.						
9. I can live a normal lifestyle, despite the pain.						
10. I can gradually become more active, despite the pain.						

Table 2

2.10 Ethical Considerations:

Ethical approval will be obtained from the Institutional Review Board of Bangladesh Health Professional Institute. Written informed consent will be obtained from all the subjects who are willing to participate in the study. Participation in this research is entirely voluntary basis and the participants have the right to withdraw from the study at any time.

2.11 Outcome measures:

Baseline outcome measures are demographic characteristics of participants such as age, gender, BMI, family size, bread winner of the family, monthly income and financial

support for study; Pain duration; Pain intensity at present moment, sitting, forward bending, standing, walking, sleeping, transferring and pain when performing day to day activities; Range of Motion of thoraco-lumbar flexion and extension; Muscle strength of thoracic spine extensors and overall scale of Pain-Self- efficacy Questionnaire. After two weeks same outcome measures will be obtained other than demographic characteristics and pain duration.

2.12 Data analysis:

Two sample t test will be used to compare the group at baseline to determine the sample characteristics in the both group will be statistically equal. To find out the significant variation in the group after the intervention again two sample t test will be used.

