3.7 Standing	
3.8 Walking	
3.9 Sleeping	
3.10 Transferring	
3.11 Performing day to day activities	

4. Range of Motion (ROM) – Base Line

Joint	Movement	ROM
Thoraco- Lumbar	Flexion	
	extension	

5. Muscle Strength – Base Line

Muscle strength of Thoracic spine extension	MMT Scale (Oxford- Grading Scale)

6. Pain- Self- efficacy Questionnaire (PSEQ) – Baseline

Please rate how confident you are that you can do the following things at present, despite the pain. To indicate your answer tap one of the options on the scale under each item, from "not at all confident" to "completely confident".

(Fill the appropriate field only)

	0 "not at all confident"	1	2	3	4	5	6 "completely confident"
I can enjoy things, despite the pain.							
I can do most of the household chores (e.g. tidying-up, washing dishes, etc.), despite the pain.							
I can socialise with my friends or family members as often as I used to do, despite the pain.							
I can cope with my pain in most situations.							
I can do some form of work, despite the pain. ('work' includes housework, paid and unpaid work).							
I can still do many of the things I enjoy doing, such							

as hobbies or leisure activity, despite pain.						
I can cope with my pain without medication.						
I can still accomplish most of my goals in life, despite the pain.						
I can live a normal lifestyle, despite the pain.						
I can gradually become more active, despite the pain.						

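### The mobility objective and hypothesis 3 concern the thoracic spine, but the outcome list and both data forms record only thoraco-lumbar motion, so the test as planned cannot support a thoracic conclusion

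*Combined protocol and SAP*

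**What the plan says.** The plan describes its mobility outcome with three different anatomical labels.

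- **Objective (Section 1.2):** "To evaluate the effectiveness of thoracic mobility exercise and manual release technique in improving upper thoracic mobility".
- **Hypothesis 3 (Section 2.5):** headed "Hypothesis about differences in thoracic mobility (Range of Motion) between control group and experimental group", with the null "There is no difference in thoracic mobility of participants between experimental and control group". Neither the heading nor the null mentions *upper* or the lumbar spine.
- **Outcome list (Section 2.11):** "Range of Motion of thoraco-lumbar flexion and extension".
- **Data forms (Annex II, pre-test and post-test):** the range-of-motion table has one joint row, "Thoraco- Lumbar", with one entry for flexion and one for extension.
- **Methods text (Section 2.9):** "Thoraco-Lumbar flexion and Extension of thoracic spine Range of Motion will be taken in the fourth section". On its plain wording, flexion is thoraco-lumbar and extension is thoracic.

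On technique, Section 2.9 says only "Measurement will be taken by using measuring tape". It gives no landmarks, body position or formula. Section 2.12 plans a two-sample t test after the intervention and names no derived thoracic variable.

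**The concern.** The variable that will be tested for hypothesis 3 is not the one that the hypothesis names. By its label, a thoraco-lumbar excursion contains lumbar movement, which neither the objective nor the hypothesis is about. Two errors are then possible:

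- a difference arising wholly or partly in the lumbar spine could be reported as a thoracic result;
- a real thoracic difference could be obscured by lumbar variation between participants.

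Section 3 already predicts that exercise will do better than manual therapy on range of motion, so a difference in that direction would readily be read as confirming a thoracic benefit. The data as planned could not show whether that reading is right.

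**Working it through.** **Is there a figure to reproduce?** No. The plan gives no expected difference, standard deviation or sample size for range of motion. The effect size of 0.5 in Section 2.6 is not tied to any named outcome. The check is therefore a comparison of the text, followed by algebra without numbers.

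**Step 1: set the labels side by side.**

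| Place | Flexion | Extension |
|---|---|---|
| Section 1.2, objective | upper thoracic (movement not named) | upper thoracic (movement not named) |
| Section 2.5, hypothesis 3 | thoracic (movement not named) | thoracic (movement not named) |
| Section 2.9, methods | thoraco-lumbar | thoracic, as worded |
| Section 2.11, outcome list | thoraco-lumbar | thoraco-lumbar |
| Annex II, both forms | thoraco-lumbar | thoraco-lumbar |

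Flexion is thoraco-lumbar wherever it is measured. Extension is thoraco-lumbar in the outcome list and on both forms, and thoracic only in Section 2.9. The forms determine what enters the data set. No form has a thoracic-only or upper-thoracic field, and no section subtracts a lumbar component.

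**Step 2: what the t test would estimate.** Assume that the recorded excursion is the sum of a thoracic part T and a lumbar part L. Write Δ for the difference in means between arms after treatment. Then

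Δ(recorded) = Δ(T) + Δ(L).

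The recorded difference equals the thoracic difference only if Δ(L) = 0. Randomisation makes the expected lumbar difference zero at baseline. It does not make the two treatments act equally on the lumbar spine, and the plan has no reading that could check this.

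**Step 3: dilution when Δ(L) = 0.** With standard deviations σT and σL and correlation ρ between the parts, the standardised effect on the recorded value is

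d(recorded) = Δ(T) / √(σT² + σL² + 2ρσTσL),

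against Δ(T)/σT on a thoracic measure. The recorded effect is the smaller one whenever σL² + 2ρσTσL > 0, that is, whenever ρ > −σL/(2σT). This holds for any zero or positive correlation. Dilution is therefore likely but not certain.

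**Step 4: can the size be stated?** It would need σT, σL, ρ and Δ(T). None is in the documents. The missing landmarks also mean that the share of lumbar motion in the tape reading cannot be inferred from the procedure. Any loss of power would come from invented inputs, and Step 3 would still cover only dilution, not false attribution.

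**The case against.** **The differences are only loose terminology.** Range of motion is one of several outcomes, the general objective is about pain, and pain measurement is untouched. Rewording alone would cure the problem. This is a fair limit on its importance. It does not remove the point, because hypothesis 3 is a named efficacy hypothesis and the form as designed cannot answer it.

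**Section 2.9 can be read as thoracic extension.** That is its plain wording, so it would be wrong to say that this section makes both movements thoraco-lumbar. The reading would rescue extension only, and Section 2.11 and both forms contradict it. It is a further inconsistency to settle.

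**Stronger reading: the arms differ in lumbar effect, to the advantage of exercise.** A reader might infer this from Annex III, where the Maitland mobilisation is described at thoracic levels only while the cat and camel exercise includes a sway of the back. The documents do not support it. The control arm also receives myofascial release to the spinal extensors, with no thoracic limit stated. The rounding phase of cat and camel is described as a stretch felt in the upper and middle back, and the cross-arm exercise keeps the lower body stable. A lumbar difference between arms is possible, but neither its presence nor its direction is shown.

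**Stronger reading: the loss of power can be quantified.** A reader might apply the 0.5 of Section 2.6 to thoracic motion and assume a thoracic share of the variance. Neither input is given for this outcome.

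**Conclusion.** The concern holds as a mismatch between objective, hypothesis and measure. If the plan is followed as written, hypothesis 3 will be tested on thoraco-lumbar motion, and a result on that measure cannot be attributed to the thoracic spine, still less to its upper part. A thoracic effect may also be diluted.

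The mismatch itself rests on the text alone. The consequences rest on one assumption, that a measure labelled thoraco-lumbar does include lumbar motion. Their size is unknown and no figure should be attached to them. The point affects the mobility outcome only. It should be corrected, and it does not put the pain comparison in doubt.

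**What to change.** Choose one of two routes and apply it throughout.

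1. **Measure what the hypothesis names.** In Section 2.9, state the tape landmarks and body positions for flexion and extension. Record the thoracic segment separately at baseline and at two weeks, with its own field on both Annex II forms. List it in Section 2.11 and name it in Section 2.12 as the variable for hypothesis 3. Change *upper thoracic* to *thoracic* in the Section 1.2 objective: a whole-thoracic reading would answer hypothesis 3 but not an objective limited to the upper part. The cost is about one extra skin mark and tape reading per visit, plus the added field. This estimate is approximate, because the present tape procedure is not described.

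2. **Claim what is measured.** Reword the objective and hypothesis 3 to *thoraco-lumbar mobility*, bring the extension wording in Section 2.9 into line with Section 2.11 and the forms, and make no claim about thoracic or upper thoracic mobility. The cost is a narrower conclusion.

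Stating the landmarks and positions is worthwhile under either route. If readings have already been taken on the present forms, only the second route remains for those participants.

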Alternate Hypothesis: $H_1: \mu_1 - \mu_2 \neq 0$

There is a difference in muscle strength of spinal extensors of participants between experimental and control group

5. Hypothesis about differences in disability of participants between control group and experimental group.

Null Hypothesis: $H_0: \mu_1 - \mu_2 = 0$

There is no difference in disability of participants between experimental and control group.

Alternate Hypothesis: $H1: \mu_1 - \mu_2 \neq 0$

There is a difference in disability of participants between experimental and control group.

2.6 Sample Size:

Sample size is Calculated by using G*power 3.1.9.4 software by assigning power 80% effective size 0.5, type I error = 0.05 and type II error = 0.2. Therefore calculated sample size was 42. Drop down rate of participants is assigned as 25 %. Therefore final sample size which obtained is 60 (Kang, 2021).

2.7 Sampling method:

Simple Random Sampling will be used as sampling technique as well as 30 Participants will be randomly allocated to each group. Participant will be allocated to the groups by using lottery method.

2.8 Data collection:

Undergraduates who are having upper back pain more than 7 days will be selected as sample and those who are having any contraindications, recent surgeries, fractures, accidents will be excluded from the students. Informed consent will be obtained from the participants. Participants will be allocated to one group by blindly select the number by lottery method. Thirty participants will be allocated randomly to each group. Allocation was concealed. Assessors will not be aware of intervention or control group and collect the demographic data, Pain assessment, Range of Motion and muscle strength at the baseline and after two weeks of intervention.

2.9 Data collection tool:

Measurement tool contains two sections such as pre-test and post-test questionnaire. In Pre-test questionnaire, there are six sections which includes personal details of the participants, pain related questions, Measurement of range of motion at base line, muscle strength at base line and pain-self-efficacy Questionnaire (PSEQ) at base line. In Post-test questionnaire, there are 4 sections which include, pain related questions

mainly pain intensity after two weeks, muscle strength after two weeks, Range of motion after two weeks and pain-self-efficacy Questionnaire (PSEQ).

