5.2.2 Post Test Questionnaire

[figure not shown]
Effectiveness of Thoracic mobility exercises versus manual release technique in minimizing mechanical upper back pain among undergraduates in Sri Lanka

Post Test Questionnaire

Code No:.....

1. Pain related questions:

In the following scale, mark a number which best describes your pain. Number “0” indicates “no pain at all”, and number 10 indicates “the worst pain ever possible”. You have to denote the number which best describes your pain in following instance and please denote the number respective to each activity in the following chart

Aspect	VAS/ Pain scale number
1.1Present Pain Intensity	
1.2Sitting	
1.3forward Bending	
1.4Standing	
1.5Walking	
1.6Sleeping	
1.7Transferring	
1.8Performing day to day activities	

2. Range of Motion (ROM)

Joint	Movement	ROM
Thoraco- Lumbar	Flexion	
	extension	

5. Muscle Strength

Muscle strength of Thoracic spine extension	MMT Scale (Oxford- Grading Scale)

6. Pain- Self- efficacy Questionnaire (PSEQ)

Please rate how confident you are that you can do the following things at present, despite the pain. To indicate your answer tap one of the options on the scale under each item, from "not at all confident" to "completely confident".

(Fill the appropriate field only)

	0 "not at all confident"	1	2	3	4	5	6 "completely confident"
I can enjoy things, despite the pain.							
I can do most of the household chores (e.g.							

tidying-up, washing dishes, etc.), despite the pain.						
I can socialise with my friends or family members as often as I used to do, despite the pain.						
I can cope with my pain in most situations.						
I can do some form of work, despite the pain. ('work' includes housework, paid and unpaid work).						
I can still do many of the things I enjoy doing, such as hobbies or leisure activity, despite pain.						
I can cope with my pain without medication.						
I can still accomplish most of my goals in life, despite the pain.						
I can live a normal lifestyle, despite the pain.						
I can gradually become more active, despite the pain.						

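### Hypothesis 2 is one difference in mean pain intensity, but pain is rated eight ways at two weeks and the plan does not say which rating or combination tests it

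*Combined protocol and SAP*

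**What the plan says.** - **Section 2.5, Hypothesis 2.** The null is "There is no difference in pain intensity of participants between experimental and control group". It has one mean per group and a two-sided alternative.
- **Section 2.9.** "VAS scale will be used to measure the intensity of pain in different situations which include present pain intensity". Seven further situations follow, each scored from 0 to 10.
- **Section 2.11.** The pain outcomes are "Pain intensity at present moment, sitting, forward bending, standing, walking, sleeping, transferring and pain when performing day to day activities". For follow-up, "After two weeks same outcome measures will be obtained other than demographic characteristics and pain duration". An overall score is named for the PSEQ; none is named for pain.
- **Annex II, section 5.2.2 (post-test form).** Items 1.1 to 1.8 take one number each; participants are told "please denote the number respective to each activity in the following chart". There is no line for a total or a mean.
- **Section 2.12.** "To find out the significant variation in the group after the intervention again two sample t test will be used". No variable, combination or multiplicity rule is given.
- **Section 2.6.** The sample size uses "effective size 0.5, type I error = 0.05 and type II error = 0.2". This is the only significance level in the plan, and the effect size is attached to no outcome.
- **Section 1.2.** The general objective is "To find out the effectiveness thoracic mobility exercise compared with manual release technique in minimizing upper back pain".

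**The concern.** A hypothesis about one mean difference needs one variable. Here there are eight, and nothing connects the hypothesis to any of them. Applied literally, the analysis section produces eight t tests for one hypothesis and gives no rule for turning eight results into one answer.

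Pain is the subject of the general objective, so the gap falls on the trial's central question. If the choice of rating, or the rule for combining ratings, were made after the results were known, the 0.05 in section 2.6 would no longer describe the false-positive risk of the pain conclusion.

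A second choice is also open. Ratings are taken at baseline and at two weeks, and the specific objectives speak of improvement. Section 2.12 does not say whether the t test compares two-week scores or changes from baseline.

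**Working it through.** **1. Count the candidate variables.** Section 2.11 lists present pain, sitting, forward bending, standing, walking, sleeping, transferring and day-to-day activities: 8 ratings. Section 2.9 and items 1.1 to 1.8 of the post-test form agree. Hypothesis 2 needs 1.

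**2. Look for a passage that closes the gap.** Section 2.9 describes the scale but ranks no rating. Section 2.11 puts present pain first but gives it no priority. Section 2.6 ties its effect size of 0.5 to no outcome, so it cannot show which rating was meant. Section 3 says that pain is measured by VAS and chooses no rating. Neither form has a summary score. Nothing closes the gap.

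**3. The plan's own error rate.** Section 2.6 sets type I error at 0.05. One test on one named variable has that rate by construction. In the favourable direction alone it is 0.05/2 = 0.025.

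**4. What an any-of-eight rule would do.** This rule is an assumption made to size the problem. If the eight ratings were independent:

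- either direction: 1 − 0.95^8 = 1 − 0.663 = 0.337
- favouring exercise: 1 − 0.975^8 = 1 − 0.817 = 0.183

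Pain ratings from one person will be positively correlated, which lowers these figures. The documents give no correlations, so a range is assumed. The simulation used no true difference, 30 per arm, eight multivariate normal ratings with common correlation r, a two-sample t test on each at two-sided 0.05, and 40,000 trials per value of r.

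| r (assumed) | any of 8, either direction | any of 8, favouring exercise | one test on the mean of 8 | one pre-named rating |
|---|---|---|---|---|
| 0.3 | 0.303 | 0.154 | 0.050 | 0.050 |
| 0.5 | 0.252 | 0.126 | 0.051 | 0.049 |
| 0.7 | 0.193 | 0.097 | 0.049 | 0.051 |
| 0.9 | 0.116 | 0.057 | 0.047 | 0.047 |

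The second column compares with 0.05, the third with 0.025.

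**5. Sensitivity.** With the 25% loss of section 2.6, 60 × 0.75 = 45 are evaluable. At 23 and 22 per arm the either-direction rates are 0.298, 0.257, 0.197 and 0.119 for the same four correlations. With ratings rounded and clipped to whole numbers from 0 to 10 (assumed mean 3, SD 2.2; 20,000 trials), they are 0.259, 0.201 and 0.133 at r = 0.5, 0.7 and 0.9. These rates cover the eight two-week scores only; the choice between score and change is not included.

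**6. What the mean of eight costs or gains.** In units of one rating's SD, the SD of the mean is √((1 + 7r)/8): 0.750, 0.859 and 0.955 at r = 0.5, 0.7 and 0.9.

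- If only one rating has a standardised mean difference (SMD) of 0.5, the mean has (0.5/8)/SD = 0.0625/SD = 0.083, 0.073 and 0.065.
- If all eight have an SMD of 0.5, the mean has 0.5/SD = 0.667, 0.582 and 0.523.

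**The case against.** The strongest reply is that the plan nowhere says one significant rating would suffice. Section 2.11 can be read as eight pre-listed outcomes, each reported in its own right, and a reader who sees all eight can judge them together. That stands. A reader might infer that the plan allows any of eight results to carry the pain claim, or that a selected result could not be told from a planned one. The documents do not support that: they give no decision rule and no sign of selective reporting. The inflated rates are therefore conditional.

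The size is also uncertain because the correlations are assumed. That too stands, but every value in the assumed range gives more than twice the single-test rate, in either direction and in the favourable direction.

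A third reply is that a mean of the eight ratings is a reviewer's preference. No section mentions one, and step 6 shows that it would nearly hide a benefit confined to one activity. For that reason it is offered only as a default.

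None of these replies supplies the missing link. Even if all eight ratings are reported, the plan does not say what pattern among them would reject Hypothesis 2.

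**Conclusion.** The gap is real and does not depend on any assumption: one hypothesis, eight recorded variables, and no stated connection between them. Its consequence is conditional. Under an any-of-eight rule at two-sided 0.05, the false-positive chance is about 30% to 12% for assumed common correlations of 0.3 to 0.9 (34% if independent), against 5%. In favour of exercise it is about 15% to 6%, against 2.5%. Normally distributed ratings and an equal correlation between all pairs are assumed.

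A reader might also infer that the overall superiority conclusion must rest on pain. The documents do not settle this. Section 1.2 and the opening of section 3 point to pain, but section 3 can also be read as expecting both treatments to relieve pain, with exercise ahead on range of motion, strength and disability. That choice belongs to the authors.

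The trial's power, and whether the PSEQ measures disability, are separate matters.

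**What to change.** Before outcome data are seen, in sections 2.11 and 2.12:

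1. Name one pain variable as the sole test of Hypothesis 2 at two-sided 0.05. The mean of the eight ratings is a reasonable default because it uses all of them; it needs a rule for unanswered items. One pre-named rating, such as present pain, controls the error equally well.
2. State whether that variable is the two-week score or the change from baseline.
3. Report all eight ratings with confidence intervals as descriptive results.
4. State which outcome carries the overall superiority conclusion, and bring sections 1.2 and 3 into line with it.

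In section 2.6, say which variable the effect size of 0.5 refers to. If outcomes have already been seen, label the choice post hoc.

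The cost is a few sentences and no new data. The main downside is dilution if the mean is chosen: an SMD of 0.5 on one activity alone shrinks to about 0.07 to 0.08. Authors who expect so localised an effect should name that rating instead.

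### Non-significant baseline t tests cannot show that the arms are equal, and a t test has no meaning for a multi-category nominal item such as bread winner

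*Combined protocol and SAP*

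**What the plan says.** Section 2.12 (Data analysis) names one method, the two-sample t test, and uses it twice: at baseline and again after the intervention. For the baseline use it states: "Two sample t test will be used to compare the group at baseline to determine the sample characteristics in the both group". The conclusion it aims at is that the "sample characteristics in the both group will be statistically equal".

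Section 2.5 makes this the first formal hypothesis of the trial. The null is "There is no difference in baseline characteristics of participants between experimental and control group", written as a difference of means equal to zero, and the alternative is two-sided.

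Section 2.11 lists the baseline characteristics. The demographic ones are "age, gender, BMI, family size, bread winner of the family, monthly income and financial" support for study. Pain duration, eight pain ratings, two range-of-motion measures, and "Muscle strength of thoracic spine extensors and overall scale of Pain-Self- efficacy Questionnaire" follow.

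The plan gives no equivalence margin, no standardised-difference rule and no method for categorical items. It does not say what follows from a significant or a non-significant baseline test. The two-week comparison is an unadjusted two-sample t test.

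**The concern.** Three things look wrong.

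1. The plan draws a conclusion of equality from a test that can only fail to find a difference.
2. Participants are allocated at random by lottery with concealment (sections 2.7 and 2.8), so any baseline difference is a chance difference. A test of whether chance produced it asks a question whose answer is already known.
3. A test on means is the only one named, although at least one listed item has no mean.

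At stake is how the trial will be read. A report that the arms were statistically equal invites the reader to accept the unadjusted two-week comparison as free of chance imbalance. The baseline test neither shows that nor corrects for it.

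**Working it through.** **Inputs.** 30 per arm (sections 2.7 and 2.8). Two-sided testing (alternative of hypothesis 1, section 2.5). Level 0.05 and planning effect size 0.5, from section 2.6: "assigning power 80% effective size 0.5, type I error = 0.05 and type II error = 0.2". Section 2.12 sets no level of its own for the baseline tests, so I assume 0.05 applies. The plan states no figure for the baseline comparison, so there is none to reproduce. The sample size calculation in 2.6 is a separate matter and is not used here beyond 30 per arm.

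**Step 1: what passes as equal.** A two-sample t test with 30 per arm has 58 degrees of freedom and critical value 2.0017. In SD units the standard error of the difference is √(2/30) = 0.2582. The largest non-significant observed difference is therefore 2.0017 × 0.2582 = 0.517 SD. A gap as large as the planned treatment effect (0.5) would be declared equal.

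**Step 2: what a real test of equality would need.** It requires a margin, and the plan gives none. For assumed margins, two one-sided tests at 0.05 each, with 30 per arm and a true difference of zero, have this power by simulation:

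| Assumed margin (SD) | Power to show equivalence |
|---|---|
| 0.2 | about 0% |
| 0.3 | about 0% |
| 0.5 | 22% |
| 0.8 | 85% |

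The trial could demonstrate equality only against a margin too wide to be reassuring.

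**Step 3: false flags.** Section 2.11 lists 7 demographic items + 1 pain duration + 8 pain ratings + 2 range-of-motion measures + 1 strength grade + 1 PSEQ score = 20. With the null true by randomisation, the expected number significant at 5% is 20 × 0.05 = 1. This expectation does not need the items to be independent.

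**Step 4: nominal items.** Bread winner is an open blank on the pre-test form (item 2.7) with no coding given. To run a t test, someone must number the categories, and the answer then depends on the numbering. Take invented counts for three categories A/B/C, 14/6/10 in one arm and 8/14/8 in the other:

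| Category placed in the middle | Arm means (codes 1–3) | t-test p |
|---|---|---|
| B (A=1, B=2, C=3) | 1.87 vs 2.00 | 0.53 |
| A (A=2, B=1, C=3) | 2.13 vs 1.80 | 0.11 |
| C (A=1, B=3, C=2) | 1.73 vs 2.20 | 0.03 |

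The same data can be called equal or unequal. A chi-square test on the same table does not depend on order and gives p = 0.08.

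Gender is different. Coded 0/1, its mean is a proportion. In simulation at 30 per arm the t test and the uncorrected chi-square test reached the same decision in every sample, with type I error between 4.8% and 5.4%.

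**Step 5: what a passed imbalance can do.** The documents give no correlation between baseline and two-week values, so I assume r from 0.3 to 0.7. A chance baseline gap of 0.5 SD, which passes the test, shifts the expected two-week difference by r × 0.5, that is 0.15 to 0.35 SD. Given that gap and no treatment effect, the two-week difference is approximately normal with mean 0.5r and variance (1 − r²) × 2/30 in squared SD units. With the unadjusted threshold of 0.517 SD and no dropout, the chance of a significant result is about 7% at r = 0.3 and 18% at r = 0.7. These figures are conditional on the gap; averaged over all randomisations the unadjusted test keeps its 5%.

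**The case against.** The strongest reply is that the baseline tests change nothing. No section attaches exclusion, covariate selection or re-randomisation to them. The two-week t test is run regardless, so the treatment estimate and its p value are the same with or without them. Baseline p values are poor reporting rather than a source of bias. That stands, and it limits the point to a wrong inference and a missed opportunity to adjust.

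Several stronger readings are tempting, and the documents do not support them:

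- *Three of the seven demographic p values are invalid.* Gender, if recorded in two categories, is handled adequately (step 4). Financial support for study is an open blank (form item 2.9) that could hold an amount, yes/no or a category. Only bread winner is clearly a multi-category nominal item.
- *Hypothesis 1 is tested by an invalid method throughout.* Hypothesis 1 is a hypothesis of difference, and for numeric items a t test is an ordinary test of it. The error is the reading of non-rejection as equality.
- *The test has only 48% power against a true 0.5 SD imbalance.* The figure is correct arithmetic for 30 per arm, but random allocation leaves no true population difference to detect. The observed difference that passes is the relevant quantity.
- *There is a 64% chance of at least one false flag.* This is 1 − 0.95^20 and requires 20 independent tests. Eight of the items are pain ratings from the same person at the same visit, so the true chance is probably lower. The expected count of about one is the safer statement.
- *The baseline tests distort the treatment comparison.* Nothing in the plan links the two.

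**Conclusion.** The point holds in limited form. The plan states a wrong rule: non-significance at 30 per arm is compatible with an observed gap of up to about 0.52 SD and cannot show equality. The test is also uninformative after randomisation, with about one false flag expected among 20 items, and it has no meaning for bread winner or for financial support if that is categorical. The harm is false reassurance; the trial's treatment estimate is not biased by it. The change is still worth making, because the plan has no other provision against chance imbalance and the baseline values needed for adjustment are already collected.

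This rests on 30 per arm at baseline, a two-sided 5% level for each baseline test, and allocation that is random as described. The conditional 7% to 18% also depends on the assumed correlations.

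**What to change.** - **Section 2.5:** delete hypothesis 1.
- **Section 2.12, baseline:** delete the baseline t tests. Present baseline characteristics by arm, as mean (SD) or median (IQR) for numeric and ordinal items and as n (%) for nominal items, with no p values and no claim of statistical equality. Define the categories for bread winner, and for financial support if it is to be categorical, before data are tabulated.
- **Section 2.12, two weeks:** for the numeric outcomes (pain ratings, range of motion, PSEQ), replace the unadjusted t test with ANCOVA: two-week value on treatment arm and the baseline value of the same outcome. Report the adjusted mean difference with its 95% confidence interval. Naming one covariate per outcome avoids choosing covariates after seeing the data and suits a trial of this size. The Oxford strength grade is ordinal and needs its own stated method; this ANCOVA is not meant for it.

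ANCOVA removes the shift shown in step 5 in expectation. It also reduces the residual variance by about the factor 1 − r², which is 0.91 at r = 0.3 and 0.51 at r = 0.7 under the assumed correlations.

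The cost is a few sentences in sections 2.5 and 2.12 and slightly more modelling. No new data, visits or participants are needed.
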